5.1.2 Subject Exclusion Criteria

The subject must be excluded from participating in the trial if the subject:

1. Is currently participating and receiving study therapy or has participated in a study of an investigational agent and received study therapy or used an investigational device within 4 weeks of the first dose of treatment.
2. Has a known history of active TB (Bacillus Tuberculosis)
3. Hypersensitivity to pembrolizumab.
4. Has a history of the following immunosuppressive conditions: bone marrow transplantation, and/or organ transplants and/or chronic rheumatic conditions that require active immunosuppressive therapy. Patients with chronic lymphoid/leukemic malignancies that have undergone treatment in the last 3 months will be ineligible.
5. Has had a prior anti-cancer monoclonal antibody (mAb) within 4 weeks prior to study Day 1 or who has not recovered (i.e., \leq Grade 1 or at baseline) from adverse events due to agents administered more than 4 weeks earlier.
6. Has had prior chemotherapy, targeted small molecule therapy, or radiotherapy within 2 weeks prior to study Day 1 or who has not recovered (i.e., \leq Grade 1 or at baseline) from adverse events due to a previously administered agent.
 - Note: Subjects with \leq Grade 2 neuropathy are an exception to this criterion and qualify for the study.
 - Note: If subject received major surgery, they must have recovered adequately from the toxicity and/or complications from the intervention prior to starting therapy.
7. Has a known additional malignancy that is progressing or requires active treatment. Exceptions include basal cell carcinoma of the skin or a separate primary squamous cell carcinoma of the skin. Patients with chronic lymphoid or leukemic malignancies are eligible with or without active disease as long as they have not had treatment within the past three months.
8. Has metastatic disease.

9. Has known history of, or any evidence of active, non-infectious pneumonitis.
10. Has an active infection requiring systemic therapy.
11. Has a history or current evidence of any condition, therapy, or laboratory abnormality that might confound the results of the trial, interfere with the subject's participation for the full duration of the trial, or is not in the best interest of the subject to participate, in the opinion of the treating investigator.
12. Has known psychiatric or substance abuse disorders that would interfere with cooperation with the requirements of the trial.
13. Is pregnant or breastfeeding, or expecting to conceive or father children within the projected duration of the trial, starting with the pre-screening or screening visit through 120 days after the last dose of trial treatment.
14. Has received prior therapy with an anti-PD-1, anti-PD-L1, or anti-PD-L2 agent.
15. Has known active Hepatitis B (e.g., HBsAg reactive) or Hepatitis C (e.g., HCV RNA [qualitative] is detected).
16. Has received a live vaccine within 30 days of planned start of study therapy.

Note: Seasonal influenza vaccines for injection are generally inactivated flu vaccines and are allowed; however intranasal influenza vaccines (e.g., Flu-Mist®) are live attenuated vaccines, and are not allowed.

5.2 Trial Treatments

The treatment to be used in this trial is outlined below in Table 2

Table 2 Trial Treatment

Drug	Dose/Potency	Dose Frequency	Route of Administration	Regimen/Treatment Period	Use
Pembrolizumab	200 mg flat dose	Q3W	IV infusion	Week 1, 4, 7, 10, 13, 16	Experimental
IMRT	60-66Gy	5 days/wk	NA	Wks 2-7 for 30 treatments	Standard of Care

5.2.1 Dose Selection/Modification

5.2.1.1 Dose Selection

The rationale for selection of doses to be used in this trial is provided in Section 4.0 – Background and Rationale.

Details on preparation and administration of pembrolizumab (MK-3475) are provided in the Pharmacy Manual.

5.2.1.2 Dose Modification

Adverse events (both non-serious and serious) associated with pembrolizumab exposure may represent an immunologic etiology. These adverse events may occur shortly after the first dose or several months after the last dose of treatment. Pembrolizumab must be withheld for drug-related toxicities and severe or life-threatening AEs as per Table 3 below. See Section 5.6.1 and Events of Clinical Interest Guidance Document for supportive care guidelines, including use of corticosteroids. There are no dose reductions for pembrolizumab. If the subject meets retreatment criteria, the full dose of 200 mg will be administered. If subjects do not meet retreatment criteria, then the dose of pembrolizumab will be SKIPPED.

Table 3
Dose Modification Guidelines for Drug-Related Adverse Events

Toxicity	Hold Treatment For Grade	Timing for Restarting Treatment	Discontinue Subject
Diarrhea/Colitis	2-3	Toxicity resolves to Grade 0-1.	Toxicity does not resolve within 12 weeks of last dose or inability to reduce corticosteroid to 10 mg or less of prednisone or equivalent per day within 12 weeks.
	4	Permanently discontinue	Permanently discontinue
AST, ALT, or Increased Bilirubin	2	Toxicity resolves to Grade 0-1	Toxicity does not resolve within 12 weeks of last dose.
	3-4	Permanently discontinue	Permanently discontinue
Type 1 diabetes mellitus (if new onset) or Hyperglycemia	T1DM or 3-4	Hold pembrolizumab for new onset Type 1 diabetes mellitus or Grade 3-4 hyperglycemia associated with evidence of beta cell failure.	Resume pembrolizumab when patients are clinically and metabolically stable.
Hypophysitis	2-3	Toxicity resolves to Grade 0-1	Toxicity does not resolve within 12 weeks of last dose or inability to reduce corticosteroid to 10 mg or less of prednisone or equivalent per day within 12 weeks.
	4	Permanently discontinue	Permanently discontinue
Hyperthyroidism	3	Toxicity resolves to Grade 0-1	Toxicity does not resolve within 12 weeks of last dose or inability to reduce corticosteroid to 10 mg

Toxicity	Hold Treatment For Grade	Timing for Restarting Treatment	Discontinue Subject
			or less of prednisone or equivalent per day within 12 weeks.
	4	Permanently discontinue	Permanently discontinue
Hypothyroidism	2-4	Therapy with pembrolizumab can be continued while treatment for the thyroid disorder is instituted	Therapy with pembrolizumab can be continued while treatment for the thyroid disorder is instituted.
Infusion Reaction	3-4	Permanently discontinue	Permanently discontinue
Pneumonitis	2	Toxicity resolves to Grade 0-1	Toxicity does not resolve within 12 weeks of last dose or inability to reduce corticosteroid to 10 mg or less of prednisone or equivalent per day within 12 weeks.
	3-4	Permanently discontinue	Permanently discontinue
Renal Failure or Nephritis	2	Toxicity resolves to Grade 0-1	Toxicity does not resolve within 12 weeks of last dose or inability to reduce corticosteroid to 10 mg or less of prednisone or equivalent per day within 12 weeks.
	3-4	Permanently discontinue	Permanently discontinue
All Other Drug-Related Toxicity ¹	3 or Severe	Toxicity resolves to Grade 0-1	Toxicity does not resolve within 12 weeks of last dose or inability to reduce corticosteroid to 10 mg or less of prednisone or equivalent per day within 12 weeks.
	4	Permanently discontinue	Permanently discontinue
Note: Permanently discontinue for any severe or Grade 3 drug-related AE that recurs or any life-threatening event. ¹ Patients with intolerable or persistent Grade 2 drug-related AE may hold study medication at physician discretion. Permanently discontinue study drug for persistent Grade 2 adverse reactions for which treatment with study drug has been held, that do not recover to Grade 0-1 within 12 weeks of the last dose. Note: Pembrolizumab does not need to be held for grade 3 dysphagia, grade 3 pain, grade 3 weight loss, or grade 3 fatigue, which are expected toxicities for head and neck radiation and will be managed aggressively by treating investigators per standards of care.			

Dosing interruptions are permitted in the case of medical / surgical events or logistical reasons not related to study therapy (e.g., elective surgery, unrelated medical events, patient vacation, and/or holidays). Subjects should be placed back on study therapy within 3 weeks of the scheduled interruption, unless otherwise discussed with the Sponsor. The reason for interruption should be documented in the patient's study record.

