4.2.3.2 Safety Endpoints

The primary safety endpoints for this study will be dose limiting toxicity (DLT). DLT for this study is defined as the occurrence of a severe adverse event (AE) listed below that is *at least possibly*

related to pembrolizumab, and occurs from the initiation of treatment thru 30 days after the final administration of the study treatment. AEs will be graded according to NCI CTCAE version 4.0. At the completion of the study, a total DLT rate will be assessed. A DLT rate of $\leq 24\%$ will be deemed acceptable and if met, the regimen will be deemed appropriate for future study in randomized studies.

The following events will be considered a DLT:

- Any \geq Grade 3 immune-related toxicity (including graft rejection), except:
 - Grade 3 dermatologic toxicity resolving to Grade 1 or lower with < 2 weeks of systemic immunosuppression
- Any \geq Grade 3 non hematologic toxicity **except**:
 - Grade 3 in-field radiation dermatitis for which IMRT is not held or held ≤ 1 week (5 fractions)
 - Grade 3 mucositis for which IMRT is not held or is held ≤ 1 week (5 fractions)
 - Asymptomatic Grade 3-4 hypomagnesemia or hypokalemia
 - Grade 3 fatigue
 - Grade 3 dysphagia or feeding tube use
 - Grade 3 weight loss
 - Grade 3 pain
- Grade 3 neutropenia with fever (oral temperature $> 39^{\circ}\text{C}$)
- Grade 3 thrombocytopenia with bleeding
- Grade 4 neutropenia with/without fever, requiring antibiotics
- Grade 4 thrombocytopenia
- Toxicity of any grade that results in inability to complete IMRT within 8 weeks

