5.2.2 Timing of Dose Administration

The first dose of Pembrolizumab should be administered week 1, the week prior to the beginning of radiotherapy (5-10 days preRT is acceptable). RT will begin the week after the initial infusion of Pembrolizumab, typically on a Monday or Tuesday. Trial treatment should be administered as per the Trial Flow Chart (Section 6.0). Trial treatment may be administered up to 3 days before or after

the scheduled Day 1 of each cycle due to administrative reasons. All trial treatments will be administered on an outpatient basis.

Pembrolizumab 200 mg will be administered as a 30 minute IV infusion every 3 weeks. Sites should make every effort to target infusion timing to be as close to 30 minutes as possible. However, given the variability of infusion pumps from site to site, a window of -5 minutes and +10 minutes is permitted (i.e., infusion time is 30 minutes: -5 min/+10 min).

The Pharmacy Manual contains specific instructions for the preparation of the pembrolizumab infusion fluid and administration of infusion solution.

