7.2.4 Evaluating Adverse Events

An investigator who is a qualified physician will evaluate all adverse events according to the NCI Common Terminology for Adverse Events (CTCAE), version 4.0. Any adverse event which changes CTCAE grade over the course of a given episode will have each change of grade recorded on the adverse event case report forms/worksheets.

All adverse events regardless of CTCAE grade must also be evaluated for seriousness.

Table 6 Evaluating Adverse Events

An investigator who is a qualified physician, will evaluate all adverse events as to:

V4.0 CTCAE Grading	Grade 1	Mild; asymptomatic or mild symptoms; clinical or diagnostic observations only; intervention not indicated.
	Grade 2	Moderate; minimal, local or noninvasive intervention indicated; limiting age-appropriate instrumental ADL.
	Grade 3	Severe or medically significant but not immediately life-threatening; hospitalization or prolongation of hospitalization indicated; disabling; limiting self-care ADL.
	Grade 4	Life threatening consequences; urgent intervention indicated.
	Grade 5	Death related to AE
Seriousness	A serious adverse event is any adverse event occurring at any dose or during any use of Merck product that:	
	† Results in death ; or	
	† Is life threatening ; or places the subject, in the view of the investigator, at immediate risk of death from the event as it occurred (Note: This does not include an adverse event that, had it occurred in a more severe form, might have caused death.); or	
	† Results in a persistent or significant disability/incapacity (substantial disruption of one’s ability to conduct normal life functions); or	
	† Results in or prolongs an existing inpatient hospitalization (hospitalization is defined as an inpatient admission, regardless of length of stay, even if the hospitalization is a precautionary measure for continued	

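### Table 3 conflicts with its own note on life-threatening events, and the cells of its diabetes/hyperglycemia and hypothyroidism rows do not agree with each other

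*Combined protocol and SAP*

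**What the plan says.** Section 5.2.1.2 makes the table binding: "Pembrolizumab must be withheld for drug-related toxicities and severe or life-threatening AEs as per Table 3 below". Table 3 has ten toxicity rows and three instruction columns: the grades at which to hold, when to restart, and when to discontinue the subject.

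- **Note under the table:** "Permanently discontinue for any severe or Grade 3 drug-related AE that recurs or any life-threatening event". It names no endocrine exception.
- **Type 1 diabetes/hyperglycemia row:** the hold cell gives new-onset diabetes or Grades 3-4. The restart cell reads "Hold pembrolizumab for new onset Type 1 diabetes mellitus or Grade 3-4 hyperglycemia associated with evidence of beta cell failure". The discontinuation cell reads "Resume pembrolizumab when patients are clinically and metabolically stable".
- **Hypothyroidism row:** Grades 2-4 stand in the hold column. The restart and discontinuation cells carry the same sentence: "Therapy with pembrolizumab can be continued while treatment for the thyroid disorder is instituted".
- **Section 7.2.4, Table 6, grading:** Grade 4 is "Life threatening consequences; urgent intervention indicated". Under seriousness, the same table gives a narrower sense of life threatening: the investigator judges that the event, as it actually happened, put the patient in immediate danger of death.
- **Section 7.2.4, Table 6, rechallenge:** planned re-exposure after a serious event that the drug may have caused needs advance approval from the clinical monitor, by reference to the protocol's dose modification guidelines.

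**The concern.** These are instructions on re-dosing after events that the protocol's own scale may class as life threatening. For the diabetes/hyperglycemia row, one line tells the site to restart and another tells it to stop for good. A site that follows either line can be recorded as deviating from the other. The protocol expects more than one site (Section 5.2.2 mentions an allowance "given the variability of infusion pumps from site to site"), so the same event could be handled differently in different places.

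The first thing at stake is patient safety. The second is whether the regimen that Section 8.1 intends to carry into a randomized trial is a single regimen, since later exposure in an affected patient would depend on which line was read.

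**Working it through.** The plan gives no figure on this point and its sample-size calculation does not enter. The check is a comparison of passages, with one small piece of arithmetic.

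**Step 1. Compare the rows with the note.** The other eight rows all order permanent discontinuation at Grade 4, as the note would. Only the two rows below do not.

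| Event | What the row says | Note, if it means every Grade 4 event | Note, if it means the narrower seriousness sense |
|---|---|---|---|
| Grade 4 hyperglycemia with beta cell failure, or new-onset diabetes at Grade 4 | Hold, then resume when stable | Stop permanently: direct conflict | Direct conflict when the investigator judges immediate danger of death |
| Grade 4 hyperglycemia without beta cell failure | First cell holds; second cell does not cover it | Stop permanently: the row gives no clear answer to set against it | Same, when so judged |
| Grade 4 hypothyroidism | Listed under hold; continuing is permitted | Stop permanently: at odds with the permission | Same, when so judged |

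**Step 2. Does the narrower meaning remove the conflict?** It does not. Table 6 describes Grade 3 as not immediately life-threatening, so for the drug-related events that Table 3 covers, an event in immediate danger of death would be Grade 4. Eight rows already stop the drug at Grade 4. Under either meaning, the note's life-threatening clause therefore changes the instruction only in the two endocrine rows, where it meets the opposite wording. The narrower meaning reduces the number of events affected but not to zero.

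**Step 3. Compare cells within rows.** In the diabetes/hyperglycemia row, the hold cell covers all Grade 3-4 hyperglycemia and the next cell only that with beta cell failure. Hyperglycemia of Grade 3-4 without beta cell failure is held by one cell and left out by the other. The restart column contains a hold instruction and the discontinuation column a resume instruction. In the hypothyroidism row, the hold column lists grades for which the other two cells allow dosing to go on.

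**Step 4. Look for a passage that decides.** Section 5.6.1 covers both toxicities but sends dose modification back to Section 5.2.1. It also ties hyperglycemia to ketosis or metabolic acidosis, a third qualifier. Section 5.9 does not settle the matter. The rechallenge rule in Table 6 leads back to the same guidelines. The notes under Table 3 do spell out an exception where one was wanted (Grade 3 dysphagia, pain, weight loss and fatigue need no hold) and give none for endocrine events.

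**Step 5. Effect on the DLT endpoint.** Section 4.2.3.2 counts pembrolizumab-related immune toxicity of Grade 3 or above, and non-hematologic toxicity of Grade 3 or above, with listed exceptions that do not include these events. The first related Grade 4 endocrine event is therefore ordinarily a DLT whichever line is followed. The DLT window (an event that "occurs from the initiation of treatment thru 30 days after the final administration of the study treatment") lengthens if dosing goes on, but that patient is already counted in the proportion.

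**Step 6. Upper limit on exposure.** Six doses are planned, at weeks 1, 4, 7, 10, 13 and 16 (Table 2). An event after the first dose leaves 6 − 1 = 5 doses that depend on the reading. One affected patient is 1/37 = 2.7% of those enrolled or 1/34 = 2.9% of those evaluable.

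**The case against.** The strongest reply is that a specific row overrides a general note, so no real conflict exists. That is a sensible way to read a table, but the documents state no such order, and the note says any life-threatening event without reservation.

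Several stronger readings are tempting, and the documents do not support them:

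- *A site cannot satisfy both the hypothyroidism row and the note.* It can. The row permits continuing and does not require it, so stopping at Grade 4 breaches nothing in the row. Only the resume instruction in the other row is directive.
- *Every Grade 4 event in these rows is in conflict.* This is not certain, given the narrower seriousness sense. Section 4.2.3.2 itself mentions asymptomatic Grade 3-4 electrolyte disturbances, so Grade 4 need not mean imminent danger in this protocol.
- *The note's clause on recurring Grade 3 events contradicts the hyperglycemia row.* Other rows, such as diarrhea/colitis and hypophysitis, also allow restart after Grade 3 and say nothing about recurrence. The note adds a recurrence rule to all of them.
- *Each site is free to re-dose on its own reading.* Serious events go to the sponsor within 24 hours (Section 7.2.3.1), and rechallenge after one needs advance approval. This stands as a real safeguard. It fits uninterrupted dosing less clearly than re-exposure, and it refers the approver to the guidelines that conflict.
- *The DLT rate is compromised.* Step 5 of the working shows that it ordinarily is not. Stopping the drug is not a PFS event under Section 8.1 either.

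The points about column placement are partly editorial. The clash between resuming and stopping does not depend on them.

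**Conclusion.** The table needs correction in two of its ten rows. The diabetes/hyperglycemia row and the note give opposite instructions for a life-threatening event, and that row's hold grades and beta cell failure condition do not match. The hypothyroidism row contradicts its own hold column, and its permission to continue is at odds with the note at Grade 4.

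The consequence is mainly for patient safety and for consistent later exposure. Five of six doses in one affected patient is a ceiling, not an estimate. The documents give no frequency for such events. The 27-patient pilot in Section 4.2.2 reports three discontinuations for immune-related events, none of them endocrine, but does not say how many endocrine events occurred. The conclusion on DLT status assumes that the event is judged at least possibly related to pembrolizumab and falls inside the window. No view is taken on which instruction is clinically right.

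**What to change.** In one amendment:

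1. Reconcile the diabetes/hyperglycemia and hypothyroidism rows with the note.
2. State in the note what a life-threatening event is (every Grade 4 event, or the narrower seriousness sense), and whether the row or the note prevails where they differ.
3. Make each cell in the two rows agree with its column heading and with its neighbors, including the hold grades against the beta cell failure condition and the Grade 2-4 entry in the hypothyroidism hold column. Check the result against the hyperglycemia wording in Section 5.6.1.

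The sponsor and the drug supplier decide which instruction stands. The cost is amendment wording and a memo to sites, with no new procedures and no additional patients.

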5.2.2 Timing of Dose Administration

The first dose of Pembrolizumab should be administered week 1, the week prior to the beginning of radiotherapy (5-10 days preRT is acceptable). RT will begin the week after the initial infusion of Pembrolizumab, typically on a Monday or Tuesday. Trial treatment should be administered as per the Trial Flow Chart (Section 6.0). Trial treatment may be administered up to 3 days before or after

the scheduled Day 1 of each cycle due to administrative reasons. All trial treatments will be administered on an outpatient basis.

Pembrolizumab 200 mg will be administered as a 30 minute IV infusion every 3 weeks. Sites should make every effort to target infusion timing to be as close to 30 minutes as possible. However, given the variability of infusion pumps from site to site, a window of -5 minutes and +10 minutes is permitted (i.e., infusion time is 30 minutes: -5 min/+10 min).

The Pharmacy Manual contains specific instructions for the preparation of the pembrolizumab infusion fluid and administration of infusion solution.

5.2.3 Trial Blinding/Masking

This is an open-label trial; therefore, the Sponsor, investigator and subject will know the treatment administered.

5.3 Randomization or Treatment Allocation

All patients will receive IMRT and Pembrolizumab as described above.

5.4 Stratification

This is a phase II trial evaluating the addition of concurrent and adjuvant fixed-dose pembrolizumab in combination with standard IMRT, in order to establish safety and estimate efficacy of this regimen to be tested in a subsequent randomized registration trial. Thirty seven patients will accrued. The primary safety endpoint will be proportion of DLTs. The primary efficacy endpoint will be 1-year PFS. The primary signal to move forward with a subsequent confirmatory randomized study will be a $\leq 20\%$ overall DLT rate and a favorable 1yr PFS compared to historical controls.

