2.0 TRIAL DESIGN

2.1 Trial Design

- This is a phase II trial evaluating the addition of concurrent and adjuvant fixed-dose pembrolizumab in combination with standard IMRT, in order to establish safety and estimate efficacy of this regimen to be tested in a subsequent randomized registration trial. Thirty seven patients will be enrolled.
- The primary safety endpoint will be proportion of DLTs. The primary efficacy endpoint will be 1-year PFS. The primary signal to move forward with a subsequent confirmatory randomized study will be a $\leq 24\%$ overall DLT rate and a favorable 1yr PFS estimate compared to historical controls.

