8.0 STATISTICAL ANALYSIS PLAN

8.1 Study Design

This is a phase II trial evaluating the addition of concurrent and adjuvant fixed-dose pembrolizumab in combination with standard IMRT, in order to establish safety and estimate efficacy of this regimen to be tested in a subsequent randomized registration trial. At the conclusion of the study, the primary safety endpoint will be proportion of DLT. The primary efficacy endpoint will be 1-year PFS. Progression-free survival (PFS) will be calculated from treatment initiation to disease progression or death from any cause or last follow up.

8.2 Justification of Design and Sample Size:

The target sample size will be 34 patients. Assuming a <10% drop out or ineligibility rate, 37 patients will be enrolled to ensure 34 evaluable patients (all evaluable patients will be analyzed). The sample size was generated based on the primary safety endpoint. DLT $\leq 20\%$ is acceptable and $\geq 40\%$ is unacceptable. If 11 or more of 34 patients experience DLT, this regimen will be considered too toxic. The significance level and power of this design are 6% and 86%, respectively. If 8 or fewer patients experience DLTs, the regimen will be deemed safe to proceed for further study. If 9 or 10 patients experience DLTs, the PI will examine the type, reversibility and duration of DLTs and a careful decision will be made whether to pursue this regimen further in this adjuvant population.

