8.3 Statistical Analysis Plan

DLT will be estimated using an exact 95% confidence interval. If 11 or more patients experience DLT the regimen will be considered too toxic. One-year PFS will be estimated using the Kaplan-Meier method and a 95% confidence interval constructed using Greenwood's method. One year PFS outcomes will be assessed overall and also separately for immunocompetent patients vs. immunosuppressed patients (e.g. CLL). These outcomes will be compared to our historical dataset for both subsets respectively. Adverse events will be tabulated by category and grade. The rates of

adverse events will be estimated using an exact 95% confidence. The relationship between 1yr PFS and baseline PD-L1 expression will be assessed using logistic regression. Immunoprofiles in peripheral blood in serial samples will be tested using random effects ANOVA. Bioinformatic analysis will be applied to all genomic and transcriptomic data.

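### Section 5.4 sets the DLT part of the go signal at 20% or less, against 24% or less in 2.1 and 4.2.3.2 and 8 or fewer of 34 (23.5%) in 8.2

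*Combined protocol and SAP*

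**What the plan says.** Four places in the current text bear on how many DLTs still allow the regimen to move forward.

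- Section 5.4: the primary signal for a confirmatory randomised study "will be a $\leq 20\%$ overall DLT rate and a favorable 1yr PFS compared to historical controls".
- Section 2.1, in nearly the same sentence: the signal "will be a $\leq 24\%$ overall DLT rate and a favorable 1yr PFS estimate compared to historical controls".
- Section 4.2.3.2, on the total rate at study completion: "A DLT rate of $\leq 24\%$ will be deemed acceptable and if met, the regimen will be deemed appropriate for future study".
- Section 8.2, as a count: "If 8 or fewer patients experience DLTs, the regimen will be deemed safe to proceed for further study". Nine or 10 DLTs go to review by the principal investigator. At the upper end, "If 11 or more of 34 patients experience DLT, this regimen will be considered too toxic", and Section 8.3 repeats that limit.

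Section 8.2 also contains the figure 20%, in another role: "DLT $\leq 20\%$ is acceptable and $\geq 40\%$ is unacceptable". These are the rates on which the sample size, significance level and power rest. On the denominator, 8.2 states that "37 patients will be enrolled to ensure 34 evaluable patients (all evaluable patients will be analyzed").

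**The concern.** Sections 2.1 and 5.4 are two copies of one decision criterion with different numbers. The gap is more than rounding: at the planned sample size it covers two possible results, 7 and 8 DLTs. Section 4.2.2 makes DLT a co-primary endpoint, and 8.2 bases the sample size on it. The sentence in question says when the regimen advances to a randomised study.

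The trial is open-label and single-arm, so DLTs are visible as they accrue. If 7 or 8 occurred, one reader could cite 2.1, 4.2.3.2 and 8.2 to say that the safety part of the signal was met, and another could cite 5.4 to say that it was not. The choice would then be made with the result known, which pre-specification is meant to prevent.

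**Working it through.** **Inputs.** Planned evaluable n = 34, enrolled 37; design rates 20% and 40%; too-toxic limit 11; safe-to-proceed limit 8 (all 8.2). Go thresholds: 20% (5.4) and 24% (2.1, 4.2.3.2). X is the number of patients with a DLT, taken as binomial(n, p).

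**Step 1: reproduce the plan's own figures.** For the rule X ≥ 11 of 34:

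- P(X ≥ 11 | p = 0.20) = 0.0620, stated as 6%.
- P(X ≥ 11 | p = 0.40) = 0.8617, stated as 86%.

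Both reproduce. Neighbouring limits do not fit: 10 gives 12.5% and 92.7%, and 12 gives 2.7% and 76.7%. So the 20% in 8.2 is the assumed true rate behind the error calculation. The observed rule in the same paragraph allows up to 8/34 = 23.5%.

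**Step 2: turn each threshold into a count at n = 34.**

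- 20% or less: 6/34 = 17.6% passes and 7/34 = 20.6% fails, so at most 6.
- 24% or less: 8/34 = 23.5% passes and 9/34 = 26.5% fails, so at most 8.
- Section 8.2 count rule: at most 8.

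The sections conflict at X = 7 and X = 8.

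**Step 3: how likely is the conflict at n = 34?** P(7 or 8) = P(X ≤ 8) − P(X ≤ 6).

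| True DLT rate | P(7 or 8 of 34) |
|---|---|
| 15% | 18.2% |
| 20% | 30.7% |
| 25% | 29.5% |
| 30% | 18.9% |

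At a true 20%, P(X ≤ 8) = 0.7731 and P(X ≤ 6) = 0.4661; the difference is 0.3070. At a true 40%, P(X ≤ 8) = 0.0341 and P(X ≤ 6) = 0.0048.

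**Step 4: other evaluable numbers.** Section 8.2 enrolls 37 and analyses everyone evaluable, so n may not be exactly 34. The last two columns give, at a true rate of 20%, the chance of a result that passes one rule and fails 5.4.

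| Evaluable n | Most DLTs, 20% or less | Most DLTs, 24% or less | 5.4 against 24% | 5.4 against the count of 8 |
|---|---|---|---|---|
| 30 | 6 | 7 | 15.4% | 26.4% |
| 31 | 6 | 7 | 15.9% | 27.8% |
| 32 | 6 | 7 | 16.3% | 29.0% |
| 33 | 6 | 7 | 16.5% | 30.0% |
| 34 | 6 | 8 | 30.7% | 30.7% |
| 35 | 7 | 8 | 14.6% | 14.6% |
| 36 | 7 | 8 | 15.0% | 15.0% |
| 37 | 7 | 8 | 15.3% | 15.3% |

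From 34 to 37 evaluable, 24% or less and 8 or fewer give the same count (8/37 = 21.6%; 9/37 = 24.3%). At 33 they separate, because 8/33 = 24.2%.

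**The case against.** The strongest reply is that the operative rule is plain. The statistical section divides every possible count into three zones (8 or fewer, 9 or 10, 11 or more), 8.3 repeats the upper limit, and 2.1 and 4.2.3.2 agree with it at 34 evaluable. The outlier is one sentence under a Stratification heading, in a trial where all patients receive the same treatment. No analysis, toxicity limit or patient's treatment depends on it. Missing the 5.4 signal is not a finding of excessive toxicity, and the signal also needs a favourable 1-year PFS, so the probabilities above describe one component and not the whole decision.

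Most of that is fair and limits the consequence. It does not remove the conflict. Section 5.4 is current text, it describes its criterion as the primary signal, and no provision ranks the sections. The 20% in 8.2 does not support 5.4 either: there it is a design rate, whereas 5.4 applies it to the overall DLT rate, the quantity that 2.1 compares with 24%.

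One qualification also stands. The agreement of 2.1, 4.2.3.2 and 8.2 holds for 34 to 37 evaluable patients, not below 34.

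**Conclusion.** The inconsistency is real, and it affects the decision threshold on a co-primary endpoint. At the planned 34 evaluable patients, 7 or 8 DLTs meets the DLT condition in 2.1, 4.2.3.2 and 8.2 and misses it in 5.4. The chance of such a result is 30.7% at a true rate of 20%, and between 18.2% and 30.7% at the four true rates tabulated from 15% to 30%. With 35 to 37 evaluable only a count of 8 conflicts, at about 15% for a true 20%. With 30 to 33 evaluable the figure is 15–17% against the 24% threshold and 26–30% against the count of 8.

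These figures assume independent patients with a common DLT probability and concern the DLT component alone. The true rates are illustrative, apart from the 20% and 40% that the plan sets. Sample size, significance level and power are not in question. The correction is small but should be made, because as written the plan gives two answers for likely results.

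**What to change.** Make one pre-specified go threshold apply throughout. The count rule in 8.2 is the natural anchor, since 2.1 and 4.2.3.2 already match it at the planned sample size. The simplest edit is to delete the percentage in 5.4 and refer to 8.2 for the DLT criterion.

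The same amendment should state the denominator. Pointing 2.1 and 4.2.3.2 to 8.2 as well would remove the divergence that appears at 33 or fewer evaluable patients.

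Optionally, the cross-reference could mention the 9–10 review zone, and 8.2 could report how the go rule behaves: 8 or fewer of 34 occurs with probability 77.3% at a true 20% and 3.4% at a true 40%.

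The cost is a wording amendment to one sentence in 5.4, or a few sentences if the other sections are cross-referred too. It needs no extra patients or data, and the stated 6% and 86% do not change.
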